#### 5.4 Secondary analysis

We will explore wider societal costs as a secondary analysis. These include participants' outof-pocket payments, lost income due to change of working status, and potential loss of productivity of unpaid carers. The difference between groups will be estimated using a regression model. The choice of regression model and included baseline covariates will be determined following the same approach as the primary analysis. The uncertainty surrounding the point estimate will also be examined by bootstrap technique.

#### 5.5 Sensitivity analyses

A series of sensitivity analyses will be undertaken to assess the uncertainties of the conclusion. To assess the impact of missing data, complete case analysis will be undertaken following the same approach of the primary analysis but only on those who have complete data on costs, QALYs, and included baseline covariates.

To examine the robustness of the MAR assumption, sensitivity analyses will be carried out using pattern mixture modelling (8). This method assumes that data are missing not at random (MNAR) and sets rules for imputing to reflect this assumption. In the current analysis, we will assume that those who have missing values at follow-ups either need more health care services (higher costs) or experience worse health (lower utility values), or both at the same time. To examine how these scenarios will affect the results based on MAR assumption, the incremental costs and QALYs will be re-estimated based on data with 1) imputed costs are increased by 20%, 40% and 60%; 2) imputed QALYs are reduced by 20%, 40% and 60%; 3) the combination of 1) and 2).

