### 3.2 Design

The FLARE RCT is a multi-centre, two-arm, parallel group, blinded, non-inferiority RCT with allocation at the level of individual. The trial is being conducted in participating Hand Trauma Centres within the UK where flexor tendon injuries are treated and with facilities to support research activity. These sites are involved in the identification of study participants and are the locations for treatment delivery.

The inclusion criteria of participants: 1) are aged 16 years and over; 2) have one digit injured only, with both FDP and FDS tendons severed; 3) have multiple digits injured but only one digit with both FDP and FDS tendons severed and any other injured digits with superficial injury or a partial tendon injury; 4) injury amendable to primary repair. Criterion 1) is confirmed at screening and the rest are confirmed in surgery.

Patients are excluded if they have multiple digits injured with both FDS and FDP tendons severed, injuries outside of zone 2, injuries affecting multiple zones, clinically infected wounds, closed flexor tendon injury, previous tendon, bone or joint injury in the affected digit, contraindication to surgery, injuries with loss of tendon substance or skin necessitating reconstruction, division of both digital arteries resulting in revascularisation of injured digit, or division of both digital nerves. Patients who do not have capacity to give informed consent or unable to complete follow-up requirements are also excluded.

The sample size is set at 310. Participants are randomised to either group at 1:1 ratio, using stratified block randomisation with randomly varying block sizes. Randomisation is implemented using a web-based system by an independent statistician at York Trials Unit (YTU), who is not involved in the recruitment of participants.

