### 5.2 Missing data

Missing data level will be described for all measures at all time points by groups and in total. Missing data patterns will be described accordingly.

Missing data will be handled based on the framework proposed by Faria et al (8). Missing values of baseline data are expected to be rare and unrelated to the group allocation. These missing values will be imputed by the mean of the measure of the pooled sample of both groups (9).

Missing values of data at follow-ups will be handled using multiple imputation with chained equation method, following Rubin's rule and assuming missing at random (MAR) (10). The association of missingness of each measure with group allocation and baseline covariates, and with observed values of the same measure at other follow-up points will be examined using statistical tests (univariate logistic regression for continuous and binary variables,  $\chi^2$  tests for discrete variables) with 0.05 as significant level. An imputation model will be developed, including all the measures necessary for the analysis or associated with missingness identified by the statistical tests. The number of imputation will be set as approximately the highest percentage figure of the missing data (9). The imputation will be performed by allocation groups.

All analyses will be conducted on the imputed dataset, unless otherwise specified.

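### The MNAR scenarios in section 5.5 never let the departure differ by arm, so they test MAR only weakly when missingness is balanced

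*SAP*

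**What the plan says.** SAP section 5.5 states the purpose of the analysis: "To examine the robustness of the MAR assumption, sensitivity analyses will be carried out using pattern mixture modelling (8"). The assumed departure is that "those who have missing values at follow-ups either need more health care services (higher costs) or experience worse health (lower utility values"), or both. This describes everyone with missing follow-up, without reference to allocation.

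The scenarios form a closed list: "imputed costs are increased by 20%, 40% and 60%; 2) imputed QALYs are reduced by 20%, 40% and 60" per cent, and "3) the combination of 1) and 2"). What is then recalculated is the comparison between arms: "the incremental costs and QALYs will be re-estimated based on data with" those altered values.

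The only by-arm element is in section 5.2: "The imputation will be performed by allocation groups". That governs how the MAR values are drawn. It does not make the later percentage shift specific to an arm.

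**The concern.** The estimates of interest are differences between arms. If the same proportional worsening is applied to imputed values in both arms, most of it drops out of the difference when the arms have similar missingness and similar imputed means. A 60% shift then sounds severe but barely stresses the comparison.

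The departure that most threatens a randomised comparison is missingness related to outcome differently in the two arms, for example if non-responders after FDP-alone repair do worse than non-responders after double repair. No listed scenario covers this. A report could then present stability across the 60% scenarios as reassurance about MNAR when that departure had not been examined.

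**Working it through.** **Inputs.** The shifts k = 0.2, 0.4 and 0.6 come from SAP section 5.5. The SAP gives no expected missingness, mean cost, mean QALY or numerical threshold, so the rest are assumptions:

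- 20% missing in each arm, with 30% and unequal rates as a range
- six-month QALYs of 0.40 in each arm, or 0.41 for FDP alone where stated
- costs of £2,800 (FDP alone) and £3,000 (FDP+FDS)
- £20,000 per QALY
- equal observed and imputed means within each arm
- a participant with missing data has the whole six-month total imputed, and covariate adjustment is ignored

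The plan has no figure of its own to reproduce on this point.

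**Formulas.** Subscript 1 is FDP alone and 0 is FDP+FDS. p is the fraction imputed and m the imputed mean.

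- Arm mean after a shift = (1 − p) × observed + p × m × (1 + k), with k negative for QALYs.
- Change in the increment, common shift = k × (p1·m1 − p0·m0).
- Change in the increment, one arm only = k·p1·m1 or −k·p0·m0.
- Net benefit (NMB) = £20,000 × dQ − dC.

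**MAR base case.** dC = 2,800 − 3,000 = −£200, dQ = 0, NMB = +£200.

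**Common combined shift, k = 0.6, 20% missing in each arm.** 0.2 × 0.6 = 0.12.

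- Costs: 2,800 × 1.12 = 3,136 and 3,000 × 1.12 = 3,360, so dC = −£224.
- QALYs: 0.40 × 0.88 = 0.352 in both arms, so dQ = 0.
- NMB = +£224. The harshest planned scenario slightly favours FDP alone.

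**Combined shift in one arm only, same inputs.**

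| Arm shifted | k | dC (£) | dQ | NMB (£) |
|---|---|---|---|---|
| FDP alone | 0.2 | 2,800 × 1.04 − 3,000 = −88 | 0.384 − 0.400 = −0.016 | −320 + 88 = −232 |
| FDP alone | 0.4 | 2,800 × 1.08 − 3,000 = +24 | 0.368 − 0.400 = −0.032 | −640 − 24 = −664 |
| FDP alone | 0.6 | 2,800 × 1.12 − 3,000 = +136 | 0.352 − 0.400 = −0.048 | −960 − 136 = −1,096 |
| FDP+FDS | 0.6 | 2,800 − 3,000 × 1.12 = −560 | 0.400 − 0.352 = +0.048 | 960 + 560 = +1,520 |

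The conclusion reverses at the mildest one-arm step. At 30% missing per arm the contrast is wider. The common 60% shift gives dC = −200 × 1.18 = −£236 and NMB = +£236. A 20% shift in FDP alone gives dC = 2,800 × 1.06 − 3,000 = −£32, dQ = 0.376 − 0.400 = −0.024 and NMB = −480 + 32 = −£448.

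**Common combined shift, k = 0.6, unequal missingness, QALY 0.41 against 0.40.** The MAR base is dC = −£200, dQ = +0.0100, NMB = +£400.

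| Missing, FDP alone / FDP+FDS | dC (£) | dQ | NMB (£) |
|---|---|---|---|
| 22% / 18% | 3,169.6 − 3,324 = −154.4 | 0.3559 − 0.3568 = −0.0009 | +136 |
| 25% / 15% | 3,220 − 3,270 = −50 | 0.3485 − 0.3640 = −0.0155 | −260 |
| 15% / 25% | 3,052 − 3,450 = −398 | 0.3731 − 0.3400 = +0.0331 | +1,060 |

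Here the common shift does bite, but its direction and size follow the imbalance in missingness, not a departure chosen in advance.

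**The case against.** A reader might go further and infer that the common shifts always cancel, so that the planned analysis cannot test MAR at all. The documents do not support that, for four reasons.

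1. **Missingness may differ by arm.** Section 5.2 reports it by group and tests its association with allocation. With 25%/15% missing, the planned shift takes net benefit from +£400 to −£260.
2. **The conclusion is not just the sign of an increment.** Section 5.3 compares the ICER with a threshold. Take dC = +£200 and dQ = +0.011 with 20% missing in each arm. The ICER is 200/0.011 = £18,182. After the common combined 60% shift it is (200 × 1.12)/(0.011 × 0.88) = 224/0.00968 = £23,140, which crosses an assumed £20,000.
3. **Imputation by arm allows imputed and observed differences to diverge.** With 20% missing in each arm, an observed QALY difference of −0.004 and an imputed one of +0.020, the MAR increment is 0.8 × (−0.004) + 0.2 × 0.020 = +0.0008. Under the common 60% reduction it is −0.0032 + 0.2 × 0.4 × 0.020 = −0.0016. The sign changes.
4. **The plan does not state that the percentage is the same in both arms.** That is inferred from the absence of any arm-specific term, though it is the natural reading.

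It is also fair to say that the listed scenarios do examine the departure the SAP names, that a complete-case analysis is planned as well, and that a 60% one-arm shift is extreme: 0.40 × 0.4 = 0.16 QALY over six months is an average utility of 0.32, against 0.80 in the other arm.

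These points limit the criticism to a weak test in some circumstances. None of them supplies a scenario in which the departure differs by arm, and the illustrated reversal needs only the 20% step.

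**Conclusion.** The point stands as a cheap improvement to a sensitivity analysis. On its natural reading, section 5.5 applies one percentage to all imputed values and leaves outcome-related missingness that differs by arm unexamined. The common shift is a weak test of MAR when missingness and imputed means are similar in the arms and the result is not near the threshold. In other cases its stringency depends on chance imbalance in missingness.

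Under the 20%-missing assumptions, the harshest planned scenario moves net benefit by £24 (+£200 to +£224), while the mildest one-arm shift moves it by £432 (+£200 to −£232). These sizes rest on assumed missingness, means and threshold. The SAP gives no QALY standard deviation, so no comparison with sampling error is made.

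The stronger inference, that the planned analysis cannot test MAR or shows robustness by construction, is not supported. The primary cost-utility analysis is untouched.

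**What to change.** In SAP section 5.5, state that the planned shifts apply to imputed values in both arms, and keep them. Add the same 20%, 40% and 60% shifts (costs, QALYs, and combined) applied to the FDP-alone arm only and to the FDP+FDS arm only. For each, report incremental costs, incremental QALYs, and net benefit or the probability of being cost-effective. Fix this before the data are analysed by arm, so that the added scenarios cannot look selected.

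The cost is more runs of the same code and one more table, with no new data. If the planned combination pairs equal percentages, the current grid is 3 + 3 + 3 = 9 scenarios and the two one-arm versions add 2 × 9 = 18. Unequal pairs of shifts and a formal tipping point are optional.

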# **6 ADDITIONAL NOTES**

The full analysis will only be performed if the trial passes the pilot stage. If a trial does not meet the target sample size in pilot stage, the sample size will not be sufficiently powered for a full cost-effectiveness analysis. The results of a full cost-effectiveness analysis based on an insufficient sample are likely to be biased. We believe that presenting such results would mislead audience. Therefore, in the case of the trial stops at the pilot stage, we will present descriptive results of the healthcare resources and EQ-5D by randomised groups, as we will have done for a standalone feasibility study.

#### SIGNATURES OF APPROVAL 7

Trial health economist: [name]

Signature: \_ [name] \_\_ Date: \_14 Apr. 25\_\_\_\_

Senior health economist: [name] \_\_\_\_\_Date: 14 4 25 an Signature: \_\_\_\_

Trial manager: [name]

Con Signature:

Date: 14/04/2025

Co-Chief investigators: [name] & [name]

Signature: [name]

Date: 28/04/2025

Signature:

Date: 28/04/2025

